#### **F. Health coaching intervention**

Health coach training. The two study health coaches were college graduates without medical training or certification but who had previously worked with patients in the public health clinic system, one as a research assistant and the other as a volunteer health coach. Both received over 100 hours of training over 3 months using a COPD health coaching curriculum specific to the study. The curriculum was comprised of two primary domains: health coaching techniques and COPD-specific knowledge. The health coaching curriculum [CEPC website] focused on five areas: (1) active listening and non-judgmental communication, (2) helping patients create self-management goals and action plans, (3) healthcare navigation, (4) medication reconciliation and adherence and (5) closing the loop (checking for comprehension by asking patients to describe the key messages in their own words). COPD-specific training covered the physiology of COPD, related comorbidities, care recommended by the Global Initiative for Chronic Obstructive Lung Disease (GOLD), prevention and management of exacerbations, and lifestyle management. Upon completion of training, coaches were required to score at least 90% on three exams assessing content knowledge and to demonstrate mastery of coaching skills through simulated role-plays and observed health coaching sessions.

Health coaching activities. Patients received health coaching for 9 months. Each health coach worked with a total of 50 patients over the two-year duration of the study, with a maximum caseload of thirty patients at any given time. Patient needs and preferences guided the frequency of contact, with a suggested minimum frequency of connecting with the patient once every three weeks. Health coaches were expected to complete an initial visit within 2–3 weeks of enrollment, to meet in person with the patient at least 3 additional times over the course of the study and to have a phone check-in call at least every 3 weeks, including within two weeks after each medical visit. Coaches were also expected to conduct at least one in-depth consultation with the study pulmonary nurse practitioner specialist (PNPS) to optimize patient care and to attend at least one medical visit between the patient and their primary care provider

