### **G. Usual care control group**

Patients randomized to usual care continued to have visits with their primary care provider over the course of the 9-month period. They received any resources their provider and their clinic offer as part of standard care, including: access to COPD educators, respiratory therapists, COPD education classes, pulmonary rehabilitation, or smoking cessation classes.

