Statistical Analysis Plan
Aides in Respiration (AIR) Health Coaching for Patients with COPD

NCT02234284

Updated September 8, 2014

Uploaded March 7, 2019

Baseline participant characteristics were compared between study arms and tested for significance using chi-square for categorical variables, t-tests for normally distributed continuous variables, and appropriate non-parametric tests for non-normally distributed continuous variables. Outcomes were compared by group assignment (intention to treat) using generalized linear mixed models (GLMMs) with a normal distribution and identity link for continuous outcomes and Poisson distribution with a log link for count outcomes. GLMMs uses random effects to account for within-participant correlations, nested random effects to account for clustering, and accommodate missing data under the assumption that the outcomes are missing at random.¹⁻⁵ In all models, baseline levels of the outcome were entered as a predictor and follow-up levels as the dependent variable, with a nested random effect of practice site to account for clustering. Hypothesis tests were 2-sided with p-values<0.05 considered statistically significant. Models used available data, while sensitivity analyses were conducted repeating primary analyses with multiple imputation procedures. Additional, exploratory per protocol and sub-group analyses were also performed, limiting patients in the coached arm to those receiving at least half of the protocol target for contacts. Differential effects (effect modification) was examined for 3 pre-specified subgroups: English vs Spanish as primary language; current smokers vs other; and COPD classification GOLD category D (high symptoms and high risk) vs other.

O. References

1. Fairclough D. Design and analysis of quality of life studies in clinical trials. New York: Chapman & Hall/CRC; 2002.
2. Little RJ and Rubin DB. Statistical analysis with missing data. New York, Wiley, 1987

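### The exploratory per-protocol analysis restricts only the coached arm by contacts received, so it is a non-randomised comparison that can show false benefit or false harm

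*SAP*

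**What the plan says.** The SAP's main comparison is by randomised group: "Outcomes were compared by group assignment (intention to treat) using generalized linear mixed models". It then describes further work: "Additional, exploratory per protocol and sub-group analyses were also performed". The rule it gives for that work is a one-arm restriction, namely "limiting patients in the coached arm to those receiving at least half of the protocol target for contacts". It gives no restriction for usual care and no weighting, matching or complier-type estimator. The adjustment stated for every model is the baseline outcome ("In all models, baseline levels of the outcome were entered as a predictor and follow-up levels as the dependent variable") plus a random effect for practice site. The significance rule is general, with no exemption for exploratory work: "Hypothesis tests were 2-sided with p-values<0.05 considered statistically significant".

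Protocol section F explains what drove the number of contacts: "Patient needs and preferences guided the frequency of contact". The only floor that goes with this is advisory: "with a suggested minimum frequency of connecting with the patient once every three weeks". Section G describes a control arm without study coaching: "Patients randomized to usual care continued to have visits with their primary care provider over the course of the 9-month period". It therefore has no contact count to which a like rule could be applied.

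**The concern.** Randomisation makes the two full arms comparable. Removing low-contact patients from one arm breaks that, because the number of contacts is settled after randomisation and partly by the patient. The control patients who would have had few contacts stay in the comparison. The estimate then mixes any effect of coaching with the difference between patients who take up contact and those who do not.

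Adjusting for the baseline outcome removes selection that acts through baseline status. It does not remove selection through motivation, social stability or health after enrolment. These matter here: section E says that homelessness, substance abuse and mental illness were not grounds for exclusion. Coached patients who leave early may also fall below the threshold, while similar controls remain eligible.

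What is at stake is the reading of the supportive evidence. A null primary result beside a significant restricted result could be taken to mean that coaching works when delivered. A restricted result pointing the other way could be taken as harm. This comparison supports neither.

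**Working it through.** The documents report no figure for the per-protocol analysis, so there is none to reproduce. The check asks how far the restricted comparison can drift when the true effect is zero.

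**Inputs from the protocol (section M)**
- Patients per arm at 9 months: 190 × 0.80 = 152, and 152 / 2 = 76, as in Table 3.
- SD of CRQ dyspnea: not stated, so back-solved from Table 2 (0.45 detectable with 80% power at 100 per arm). SD = 0.45 / [(1.960 + 0.842) × √(2/100)] = 1.136.
- Consistency of that SD: power for a difference of 0.5 is 0.876 at 100 per arm (stated .88) and 0.775 at 76 per arm (stated .78). The detectable difference at 76 per arm is 0.516 (stated 0.51). This shows agreement with the tables; it does not confirm the SD independently.

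**Assumptions (the documents give none of these)**
- Fraction f of coached patients meeting the contact rule: 0.5 to 0.8.
- Correlation ρ between propensity for contact and the part of the 9-month outcome not explained by baseline: 0.1 to 0.3 in size, of either sign.
- Baseline-to-follow-up correlation 0.6, so the residual SD is √(1 − 0.6²) = 0.8 outcome SDs.
- Normal distributions and no site effect.

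**Bias.** In points, bias = ρ × φ(c)/f × 0.8 × 1.136, where c is the (1 − f) normal quantile. The factor φ(c)/f is 0.798 at f = 0.5, 0.497 at f = 0.7 and 0.350 at f = 0.8.
- Smallest (f = 0.8, ρ = 0.1): 0.1 × 0.350 × 0.8 × 1.136 = 0.03 points.
- Middle (f = 0.7, ρ = 0.3): 0.3 × 0.497 × 0.8 × 1.136 = 0.14 points.
- Largest (f = 0.5, ρ = 0.3): 0.3 × 0.798 × 0.8 × 1.136 = 0.22 points.

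Against the protocol's MCID of 0.5, the range is 0.03/0.5 = 6% to 0.22/0.5 = 44%.

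**False-positive rate.** In residual SDs, SE = √(1/76 + 1/(76f)). With d = ρ × φ(c)/f / SE, the rate is Φ(d − 1.96) + Φ(−d − 1.96).
- f = 0.8, ρ = 0.1: d = 0.035/0.172 = 0.20; rate about 0.055.
- f = 0.5, ρ = 0.3: d = 0.239/0.199 = 1.20; rate about 0.23.

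**Simulation with baseline adjustment** (76 per arm, zero effect, 4,000 runs per cell), percentage of restricted comparisons significant at two-sided 0.05:

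| Retained | ρ = 0 | ρ = 0.1 | ρ = 0.2 | ρ = 0.3 |
|---|---|---|---|---|
| 50% | 4.9 | 7.4 | 13.4 | 21.8 |
| 70% | 5.1 | 5.8 | 9.1 | 12.8 |
| 80% | 5.2 | 5.4 | 7.5 | 8.5 |

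The intention-to-treat test on the same data stayed at 4.3-5.5%. With positive ρ, nearly all of the excess is false benefit. With ρ = −0.3 and 70% retained, the bias was −0.12 SD (−0.12 × 1.136 = −0.14 points) and 13.3% of runs were significant, nearly all as false harm.

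**The alternative.** Two-stage least squares with assignment as instrument, under the same zero-effect conditions, rejected in about 4-6% of runs, with mean estimates within 0.01 points of zero. The standard error rose from about 0.16 to 0.21 points at 70% retained.

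**The case against.** The strongest reply has four parts.

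1. **The analysis is exploratory and the main analysis is by assignment.** This stands. The primary estimate and its error rate are not touched, and nothing in the documents promotes the restricted result. The label does not remove the bias, however, and the general p-value rule still applies to it.

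2. **The direction is not known.** This also stands. A reader might infer that the restriction flatters coaching. The documents do not support a one-way reading. Section F names needs as well as preferences and asks for a call after each medical visit, so patients with more visits could accumulate more contacts. It also says home visits went mostly to patients with transport or mobility difficulties. Need-driven contact would bias against coaching.

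3. **The size rests on assumed inputs, and baseline adjustment reduces it.** This is right. Applying the correlation to the whole outcome, without allowing for the baseline term, would give 0.04-0.27 points. The working above uses only the residual part and gives 0.03-0.22. The 23% is the worst corner; at 70-80% retained and ρ of 0.1-0.2 the simulated rate is 5.4-9.1%.

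4. **A complier-average estimate has its own assumption.** It supposes that coached patients below the threshold gained nothing, yet section F has the pulmonary nurse practitioner sending recommendations to the primary care provider, generally without seeing the patient. If such patients got half the effect, dividing the intention-to-treat estimate by p overstates the effect by (1 − p)/(2p): 21% at p = 0.7 and 50% at p = 0.5. This stands as a reason to state the assumption and test it. It does not rescue the restricted comparison, which can be biased even when coaching does nothing. The complier estimate is not.

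That usual care has no contacts to restrict on explains why the rule is one-sided, but does not make the comparison fair.

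**Conclusion.** The concern holds in limited form. The restricted comparison is non-randomised and its bias can run either way. With no true effect, 50-80% retained, a residual correlation of 0.1-0.3 in size and a baseline-to-follow-up correlation of 0.6, the bias is about 0.03-0.22 CRQ dyspnea points and the false-positive rate about 5-23%. If contacts were unrelated to prognosis, the error rate would stay near 5%. The retained fraction and both correlations are assumptions, and the SD is back-solved from the power table.

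A reader might go further and infer that the trial's main conclusion is compromised. The documents do not support that: the intention-to-treat analysis keeps patients by assignment and is separate from this one. The point is an inexpensive improvement to supportive evidence.

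**What to change.** For continuous outcomes, replace the restricted comparison with a complier-average estimate:

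- Keep both arms as randomised and use assignment as the instrument for receiving at least half of the target contacts.
- Adjust for baseline outcome and site.
- Handle missing 9-month outcomes with the multiple imputation the SAP already plans. Section M expects 20% attrition, and section L reports higher 9-month completion in usual care.
- For exacerbations, which the SAP models as Poisson with a log link, use a version suited to counts.
- State the assumption that patients below the threshold gained little. Add a sensitivity analysis with number of contacts as the exposure, noting that it assumes a linear dose-response.
- State which count served as the contact target. Section F can be read as about 13 contacts (39 weeks / 3) or about 17 (13 + 1 initial + 3 in person), so half is 6.5 or 8.5.

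If the restricted comparison is kept, report it as descriptive and non-randomised, of uncertain bias direction, without a p-value.

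The cost is wider intervals and the stated assumption. No new data are needed. Because the SAP is written in the past tense, this may in practice be a reanalysis and should then be labelled as such.
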